## **8.2 Effectiveness endpoints**

Established endpoint measures in axSpA and PsA will be used to describe the long-term effectiveness of treatments. The principles described above for the analysis of safety endpoints will also be followed in a similar manner regarding effectiveness endpoints (for examples see [45-47]).

One important outcome measure is work participation. It can already be addressed after enrolment of roughly 500 patients in the treatment and control groups each. Another one is the investigation of the influence of chronic changes on the one hand and disease activity on the other hand on the functional capacity and the quality of life of the patients. This also requires only a limited sample size but needs the data collection of radiographic and MRI data. RABBIT-SpA will further contribute to the ongoing discussion of the interaction between suppression of signs of inflammation, development of fatty lesions and chronic changes (syndesmophytes) in axSpA. These are only three examples of clinical and social outcomes which should be addressed with RABBIT-SpA.

## **8.3. Dropout analyses**

In case patients are lost to follow-up, the reasons for study non-completion will be determined and comparisons of drop-outs and non-drop outs will be performed.

## **9. Informed consent / ethical considerations**

The treating rheumatologists will recruit and enroll patients to RABBIT-SpA according to the inclusion criteria. Neither the DRFZ nor the companies will influence the treatment decisions taken by the physicians documenting the patients. They will inform the patients about the aims, the methods of data gathering and the scientific use of the data. Each patient will receive a written information leaflet. After having received the information, the patient will be asked to sign an informed consent (IC) form. It contains consent with the storage of pseudonymised data in the database and the use of anonymised data for publications. It will also explain the process of vital status research by the trustee. Further, pseudonymised data can be used for safety reporting to the companies. The signed IC form remains with the treating physician, the patient receives a copy.

The original study protocol dated July 22, 2016, was reviewed and approved by the Ethics Committee of the Charité Medical School in Berlin. This amendment and all further amendments will also be submitted to this Ethics Committee. Data will be archived for at least ten years after the end of the study at the DRFZ in Berlin. No selected data or entire data sets will be disclosed without authorization to third parties, including the companies, but the companies will receive upon request additional analyses on their own products separate from the joint evaluations. The study management, advisory board and companies will decide jointly whether data may be passed on for collaborative analysis (international studies).

## **10. Description of the IT system and the procedures of data collection**

For data collection, the RABBIT-SpA online tool for physicians and patients will be used. It has been developed by Tembit Company (today: Serrala), Berlin, together with the DRFZ. The physician will sign a contract with the DRFZ and will then be authorized to use the system (Fig. 1). After informed consent, the physician will register the patient in the RABBIT-SpA database via a secure data connection (SSL) (Fig. 2). The physician will document the data in the practice or clinic while the patients can choose to use the online tool at home or in the practice/clinic. The patient questionnaires can also be printed out, filled out by the patients on paper and then typed into the

online system by the physician/study nurse in case the patient does not want to use the online system by him-/herself.

The pseudonymisation service (PSS) generates a unique pseudonym for each individual patient. After the physician has entered the diagnosis (axSpA or PsA), the respective questionnaires for physicians and patients are automatically provided. The patient receives an email with preliminary log-in data and can then log into RABBIT-SpA via an internet browser (Fig. 2). The preliminary password will need to be changed by the patient and the patients can then answer the first questionnaire.

## Registration of physicians

[figure not shown]

Figure 1: Registration of physicians

# Registration of patients

[figure not shown]

Figure 2: Registration of patients

At follow-up, the physician and patient log into the system and are provided with the questionnaires for the respective time points. In case the questionnaires are not answered in time, the physician and the patient are sent reminders.

The questionnaires can be completed with additional data (e.g. lab results) within a time period defined by the PIs. After this time period, the questionnaires are automatically transmitted.

## 11. Termination of study participation

The patients have the right to terminate study participation at any time point without giving reasons. In case a patient decides to terminate participation in RABBIT-SpA, the patients can unsubscribe either via their own profile or by informing their treating rheumatologist. They can decide whether they want to simply unsubscribe from RABBIT-SpA and terminate participation or whether they want to withdraw the informed consent. In this case, the personal data (name, first name, maiden name, date of birth and place of birth as well as postal address and e-mail) will be deleted and thus the data is fully anonymised.

## **12. Data protection**

### **12.1 Role definition and access to the data**

The collection, transfer, storage and analysis of the data follows the German data protection legislation. Only authorized personnel has access to the data after having given written agreement to observe the legislation concerning data protection, data security and confidentiality. The data are protected against unauthorized access and not transmitted to any third party.

Access to the data depends on individual roles. The following roles exist:

- Technical administration of database
- Trustee to re-identify a patient in case of death (DRFZ co-worker, not involved in RABBIT-SpA)
- Study leadership (PIs) and co-worker at the DRFZ
- Participating physician / study nurse
- Participating patient

The technical administration of the RABBIT-SpA application, the PSS and the database will be provided by Serrala Cloud Solutions GmbH (formerly Tembit Software GmbH) who will update the application or database, if necessary. Serrala has no access to the patient data. If necessary, staff from Serrala will be authorized by the PIs to get access to the RABBIT-SpA server. All work follows the four-eye principle. An authorized person at the DRFZ will receive limited, administrative access to the database in order to initialize the register.

As a matter of principle, the PIs and co-workers of RABBIT-SpA will have no access to patient identifying data such as last name, first name, date of birth or place of residence. They will use exclusively pseudonymised data for monitoring, data management and analysis.

The participating physicians and their authorized co-workers (study nurses) will have access to data entered by themselves. They see a list of their patients with names as well as a list of missing or incomplete questionnaires which they have to complete. After having submitted data, the physicians as well as the patients cannot change their data.

If no information has been received for at least two time points of follow-up the physician will be asked via the system by the DRFZ team whether the vital status of the patient is known. If the patient has died the physician is asked to report the date and cause of death to the study coordinating office. If no further information can be provided by the physician, the trustee will get special access to the system. This function is solely subject to the trustee role. The trustee will be able to re-identify the patient by receiving the name and address from the system. He will contact the patient to get information about the vital status. If this was unsuccessful, the trustee will contact authorities in order to establish the vital status of the patient. RABBIT-SpA will log every data entry of this process. RABBIT-SpA offers access to this respective patient exclusively for the trustee. The trustee is not allowed to get another user role in RABBIT-SpA. In case of death of the patient, the trustee will provide the gathered information via the system, i.e. in a pseudonymised way, to the study coordinating office.

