## **2. Aims of the study**

Major aims are:

1. To describe the long-term effectiveness of treatment with targeted therapies, e.g. drug survival, effectiveness of treatment combinations, level of disease activity achieved.

2. To study the long-term safety of all available targeted therapies for axSpA and PsA  
This includes the observation of all adverse events (serious and non-serious) in order to assess the overall safety profile. Specific emphasis will be laid on “events of interest” (see 8.1.1 below).
3. To investigate the interplay between disease activity, comorbid conditions and safety outcomes, the interplay between disease activity, radiographic changes and functional outcomes and to explore the role of treatment in these interactions.
4. To describe selected direct and indirect costs of targeted therapies compared to standard therapy. This includes the description of health care consumption and work disability.

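### The enquiry about silent patients covers vital status and death but not non-fatal SAEs or malignancies since the last form, and no closing safety form is described for patients who unsubscribe

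*Protocol*

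**What the plan says.** Aim 2 (section 2) is the long-term safety of all targeted therapies: "This includes the observation of all adverse events (serious and non-serious) in order to assess the overall safety profile". The flow chart in section 6 places adverse events on the physician's form, at month 3 and then every 6 months.

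Section 12.1 sets out what happens when a patient goes silent, meaning that nothing has arrived for two or more scheduled visits: "the physician will be asked via the system by the DRFZ team whether the vital status of the patient is known". The subject of that enquiry is vital status. For a death the next step is: "If the patient has died the physician is asked to report the date and cause of death to the study coordinating office". If the physician cannot help, the trustee re-identifies the patient: "He will contact the patient to get information about the vital status". The trustee then turns to the authorities if needed. The only return of information to the study office that is described is for a death.

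Section 11 deals with patients who leave actively: "The patients have the right to terminate study participation at any time point without giving reasons". As to the route, "the patients can unsubscribe either via their own profile or by informing their treating rheumatologist". The section mentions no final form and no final question to the physician.

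Section 8.3 says that for patients lost to follow-up "the reasons for study non-completion will be determined and comparisons of drop-outs and non-drop outs will be performed". Section 15 gives the medical data managers the task of dropout research.

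**The concern.** A patient who is hospitalised, or is diagnosed with cancer, and then stops attending may leave no physician form for that interval. The register does return to the physician, and sometimes to the patient, but the enquiry it describes concerns survival. A fatal event in the gap is sought, while a non-fatal one in the same gap is not. A patient who unsubscribes through the online profile need not involve the physician at all.

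The crude incidence rates of events of interest that go to the companies every six months (section 7.4) are at stake, as are later publications on serious infections, cardiovascular events and malignancies. If serious illness is one reason for leaving, the missing events are not a random sample. Section 8.1 lists attrition and selection among the sources of changing risk, but no model recovers an event that was never recorded. The comparison in section 8.3 rests on data collected before departure, so it cannot show what happened afterwards.

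**Working it through.** The protocol gives no attrition rate, SAE rate or bias estimate, so there is no stated figure to reproduce. The check has three parts.

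**1. Does any described step seek a non-fatal event after the last form?**

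| Step | Section | Seeks an unreported non-fatal SAE? |
|---|---|---|
| Enquiry after two silent time points | 12.1 | No: vital status; date and cause if dead |
| Trustee contact | 12.1 | No: vital status |
| Unsubscribing | 11 | No closing form described |
| Automatic SAE query | 7.3 | No: generated only after an SAE has been saved |
| Reminders, list of open forms | 10, 12.1, 13.2 | Indirectly, while the form is open; it is then auto-committed, and submitted data cannot be changed |
| Missing-data queries | 13.1 | Possibly; generic, no such content stated |
| Reasons for non-completion, dropout research | 8.3, 15 | Possibly; no link to section 7.3 stated |
| Hospital or practice information systems | 12.3 | No: access not intended |

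Several steps could bring an event to light. None is described as asking for it.

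**2. How long is the gap?** Section 4 gives visits at months 0, 3, 6, 12, 18 and so on. Gap = month of second missed visit minus month of last form:

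- last form at baseline: 6 − 0 = 6 months
- last form at month 3: 12 − 3 = 9 months
- last form at month 6: 18 − 6 = 12 months, and 12 months from then on

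The section 7.4 risk window for SAEs other than deaths and malignancies is 3 months. The gap is therefore 6/3 = 2 to 12/3 = 4 times that window, so an SAE assignable to a drug can fall wholly inside it.

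**3. What could this do to a rate?** All inputs here are assumed. Take 80 recorded SAEs in 1000 patient-years and 100 leavers, of whom 5, 10 or 20 have one unrecorded SAE (m). Let p be the gap person-time not already in the denominator. Then

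understatement = 1 − [80/1000] ÷ [(80 + m)/(1000 + p)].

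| | m = 5 | m = 10 | m = 20 |
|---|---|---|---|
| p = 0 (gap already counted) | 5/85 = 5.9% | 10/90 = 11.1% | 20/100 = 20% |
| p = 50 (100 × 6 months, censored at last form) | 1 − 84/85 = 1.2% | 1 − 84/90 = 6.7% | 1 − 84/100 = 16% |
| p = 100 (100 × 12 months, censored at last form) | 1 − 88/85 = −3.5% | 1 − 88/90 = 2.2% | 1 − 88/100 = 12% |

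In the first cell of the last row the recorded rate (80) exceeds the full rate (85/1100 = 77.3 per 1000), so the direction reverses. With censoring at the last form, the rate is understated only if events in the gap are more frequent than in observed time. The break-even is 0.08 × p, that is 4 events for p = 50 and 8 for p = 100.

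For a rate ratio with p = 0, observed/true = (1 − q_index)/(1 − q_control), where q is the assumed share of SAEs lost. Equal loss gives 1.00; 5% versus 20% gives 0.95/0.80 = 1.19; 20% versus 5% gives 0.80/0.95 = 0.84.

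**The case against.** The strongest reply is that this argues from silence. The enquiry stands in a section on data protection and roles, and mainly explains why a trustee may re-identify a patient. It does not claim to be the whole procedure for lost patients. Query wording and closing forms often sit in operating documents. The protocol also sends reminders, obliges physicians to complete missing forms, queries missing data and assigns dropout research. It lets a new rheumatologist who is or becomes registered continue the record (section 12.2).

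Much of this stands, and it rules out several stronger readings:

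- A reader might infer that the register asks only whether the patient is alive and that these events are never collected. Date and cause of death are also requested, so fatal malignancies can be captured, and the steps above may recover other events.
- A reader might infer that SAE collection ends when a patient stops filling in questionnaires. It does not: SAEs come from the physician, and the trigger is that no information arrives at all.
- A reader might infer that section 8.3 cannot be carried out because patients may leave without giving reasons. That right concerns those who actively terminate; section 8.3 concerns patients lost to follow-up, and physicians can report reasons.
- A reader might infer that rates are biased downward, most of all for drugs with high attrition. The protocol gives no data for this, and patients stay under observation when treatment changes, so stopping a drug is not leaving the register.

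What the reply does not supply is a step that asks for the events. The one contact specified for a silent patient has a stated content, and non-fatal SAEs are not in it.

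**Conclusion.** The point holds as a gap in data collection. As described, the lost-contact enquiry seeks deaths but not non-fatal SAEs or malignancies since the last form. Section 11 describes no closing safety form, and the reasons for non-completion have no stated route into SAE reporting. Non-fatal events around departure can be missed over a gap of 6, 9 or 12 months, depending on when the last form was filed.

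Crude rates may be understated if departure is related to the event. Neither size nor direction can be computed from the protocol: both depend on attrition, on how often an event accompanies departure, and on whether gap person-time is counted. The percentages above are illustrations on assumed inputs. Rate ratios are affected only if the loss differs between groups.

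Later analysis cannot replace the missing data, which makes this worth changing in the protocol. It does not undermine the register as a whole.

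**What to change.** Extend the existing physician query in section 12.1 to ask, for the time since the last completed form:

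- any SAE or malignancy (yes, no or unknown, with date and diagnosis)
- date of last known contact
- reason for stopping

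Route any SAE reported there into the section 7.3 process, and use the reason field to supply section 8.3. End person-time for non-fatal events at the date to which SAE status is known, so that events and denominator cover the same period. Where consent permits, send the same short form to the physician when a patient unsubscribes without withdrawing consent.

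The cost is a few added fields in a query already sent, one short form per unsubscribing patient, and a small burden on sites. Under section 9 the amendment goes to the Ethics Committee. The consent wording, which is not in the text at hand, must be checked before physicians are asked about patients who have ended participation.

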## **12.2 Pseudonymisation**

After having received informed consent, the physician registers the patient via a secure internet connection in the RABBIT-SpA database. The physician enters a quintuple, consisting of name, first name, maiden name, date of birth and place of birth as well as postal address and e-mail of the patient and the main diagnosis. The personal data are recorded in encrypted form. With the registration, an automatic encrypting program (pseudonymisation service, PSS) is started.

The PSS generates a pseudonym which does not allow any conclusions to be drawn as to the identity of the patient. The PSS contains a „fuzzy recognition tool“ for the automatic recognition of typos. The PSS also recognizes whether a patient is already registered in the RABBIT-SpA database and gives feedback. The PSS does not allow double registration of patients except in case of changing the treating rheumatologist. If the patient switches to a physician who already participates in RABBIT-SpA, the new physician enters the quintuple and thereby identifies the patient in the database. The patient confirms that this physician is authorized to enter data for RABBIT-SpA. The new physician gets access to the current questionnaires and the history of the physician and patient data but cannot change previous entries. If the new physician is not yet registered in RABBIT-SpA, he/she has to register first. The previous physician receives a message from the system and cannot access the data that are entered by the new physician.

The PSS in RABBIT-SpA was developed by Tembit Software GmbH (today: Serrala) according to the principles of the „Telematik Plattform“ as well as G3P Good Privacy Protection Practice in Clinical Research. It has been used in the framework of the BMBF funded project "SmartSenior" in 2012 and is currently used in the Rhekiss register. Both applications have been approved by the Ethics Committee of the Charité University Medicine Berlin.

## **12.3 Software and Server**

The Rabbit-SpA Register is based on the internet application mdoc (mdoc=medical documentation system). The Rabbit-SpA Server is hosted by a certified provider (BSI, ISO27001) in Germany that guarantees an operation conform to German data protection legislation. Contemporary security measures protect the server reliably from external intrusions.

Rabbit-SpA access to Hospital Information Systems (HIS) or Practice Information Systems (PIS) is not intended.

Data are stored in a database on a server hosted by an authorized German provider. Patient related data are separated from clinical data. Patient related data (quintuple) are stored in encrypted manner. Based on the one-way-encryption SHA-256 (Secure Hash-Algorithm) there is no reference between the pseudonym and the patient data inside the database.

The selected host fulfills all requirements and provides all necessary certificates to store personal medical data conform to German data protection law.

## **13. Study procedures**

Participating physicians will be provided with the study protocol, a contract with the DRFZ, information on the access to the e-CRF, precise instructions how to use the e-CRF, how to inform the patients and achieve informed consent, and support in the implementation of the study.

### **13.1 Queries**

In case of (serious) adverse events and in case of implausible or missing data it will be necessary for the DRFZ to send queries to the treating physician. This will be done with a software aided process using the patient's pseudonym and a system generated unique "query number". The rheumatologist will be informed about the query. The query (with full name of the patient) appears in his RABBIT-SpA profile. The physician can then answer the query in agreement with the data protection requirements.

### **13.2 Monitoring**

The physician has access to the list of his patients and the open questionnaires. The study leadership decides about the period of validity of questionnaires. After this time period, the questionnaires will be auto-committed.

The patient will be regularly informed about new questionnaires in his RABBIT-SpA document center via email and asked to answer them.

The study leadership has access to a list that shows the current state of progress for all questionnaires for each participating rheumatologist. In addition, the modules have inbuilt plausibility checks in order to avoid implausible or missing data as far as possible.

## **14. Expected numbers of enrolled patients**

To achieve the aims of RABBIT-SpA, the team at the DRFZ will take several measures to motivate rheumatologists to enroll patients into RABBIT-SpA. However, since RABBIT-SpA is an observational study of routine rheumatologic care in Germany, the number of patients under a particular drug who will be enrolled is not manageable by the study centre. Nevertheless, we aim at enrolling at least 500 patients under each of the index drugs until end of 2019 plus two control cohorts (axSpA and PsA) of 1000 patients each.

## **15. Personnel**

A study physician will be responsible for the study supervision, coding adverse events and compiling reports. A statistician will be responsible for the data analysis and statistical testing. Medical data managers will be responsible for study monitoring (organization of schedules, coding, dropout research, etc.). The medical data managers continuously monitor the e-CRFs and issue queries in case of incomplete or implausible information.

